## 26 PUBLICATION POLICY

The Sponsor retains ownership of all data arising from the trial, however the trial team have unfettered access to the data for follow-up studies and cross tabulation of genomics and other data from the ChOPIN study using the same patient cohort.

The intention is to publish this research in a specialist peer reviewed scientific journal on completion of the study. The results may also be presented at scientific meetings and/or used for a thesis. The AspECT Chief Investigator and Trial Management Group will be involved in reviewing drafts of the manuscripts, abstracts, press releases and any other publications arising from the trial and retain final editorial control. Individuals wishing to present or publish material arising from AspECT must not do so without the written approval of the Chief Investigator and Trial Management Group.

The TMG are responsible for deciding which investigators and scientists are added to the paper. Local investigators qualified for authorship for the main paper by recruiting a minimum of 25 patients and having a data return rate of 95% or greater or for all clinical papers including translational studies related to AspECT by recruiting 50 patients and having a data return rate of 95% or greater.

Authors must acknowledge that the study was Sponsored by the University of Oxford and performed with the support of the Oncology Clinical Trial Office.

1. Introduction

This document details the proposed presentation and analysis for the main paper(s) reporting results from the CTAAC funded multicentre randomised controlled trial of aspirin and esomeprazole in the prevention of adenocarcinoma or high grade dysplasia in Barrett's metaplasia (AspECT). The results reported in these papers should follow the strategy set out here. Subsequent analyses of a more exploratory nature will not be bound by this strategy, though they are expected to follow the broad principles laid down here. The principles are intended to establish the rules that will be followed, as closely as possible, when analysing and reporting the trial.

This analysis strategy should be available on request when the principal papers are submitted for publication in a journal. Suggestions for subsequent analyses by journal editors or referees will be considered carefully, and carried out as far as possible in line with the principles of this analysis strategy; if reported, the source of the suggestion will be acknowledged.

Any deviations from the statistical analysis plan will be described and justified in the final report of the trial. The analysis should be carried out by an identified, appropriately qualified and experienced statistician, who should ensure the integrity of the data during their processing. Examples of such procedures include quality control and evaluation procedures.

Version 0.4 of this analysis plan was released for the first DSMC. Since the trial is of a longer duration, it is expected that some of the analysis may be updated with the agreement of the TSC and DSMC. Version 1.0 of the analysis plan was released before the 4 year interim analysis. Version 2.0 is due to be the final version used to analyse the primary aim. Any additional analysis carried out will be mentioned in the published paper of the trial results.

2.1 Objectives

Primary OBJECTIVES:

- To assess whether intervention with aspirin results in a decreased rate of all causes of mortality or conversion rate from Barrett's metaplasia (BM) to adenocarcinoma or high grade dysplasia.
- To assess whether high dose PPI therapy results in a decreased rate of all causes of mortality or conversion rate from Barrett's metaplasia to adenocarcinoma or high grade dysplasia.

Secondary OBJECTIVES:

- To assess whether intervention with aspirin results in decreased high-grade dysplasia, in decreased all cause mortality, in decreased oesophageal cancer incidence and in decreased cause-specific mortality when each is considered separately
- To assess whether intervention with high dose PPI results in decreased high-grade dysplasia, in decreased all cause mortality, in decreased oesophageal cancer incidence and in decreased cause-specific mortality when each is considered separately
- To assess whether there are clinical and molecular risk factors which can be identified in BM for the development of Barrett's Adenocarcinoma (BA).
- To assess the cost effectiveness of aspirin and/or PPI treatment in the prevention of BA.
- To assess whether intervention with PPI and/or aspirin induces changes in the expression of molecular markers for BA. To assess the genomics of aspirin sensitivity (efficacy and side effects)
- To assess how quality of life is affected by the different treatments.
- To assess what the biological risk factors are for cardiac disease and aspirin resistance.
- To assess gender differences in outcomes.

Exploratory aims

1. To assess aspirin's role on the development of colorectal adenomas and cancer.
2. To collect and bank samples for use in future ethically approved studies

AspECT

A phase III randomised study of Aspirin and Esomeprazole chemoprevention in Barrett's metaplasia

Funded by CR-UK, MRC, UHL and NCI

ISRCTN No.85156844

Exploratory uses of the data

1. Describe Barrett's length over repeat biopsies and investigate a change in length from baseline to 2 years between treatment groups.
2. Can intervention with aspirin result in a lower stage of adenocarcinoma ?
Can intervention with PPI result in a lower stage of adenocarcinoma ?
3. Does adjustment for Oesophagectomy, Ablation therapy, Endoscopic mucosal resection change the treatment effect ?
4. Is the event rate different for those previous users of aspirin who were not randomised to it compared to previous users who continued with aspirin as their randomised treatment?
5. Investigation of the hypothesis that aspirin will have a chemopreventive effect on all epithelial cancers using the same mechanism it does to reduce oesophageal cancer, however, high dose PPI therapy may arguably increase colon cancer incidence as gastrin levels increase and this hormone is a known stimulant for colon cancer in mice.
6. Look for a dose/time response effect for aspirin and for esomeprazole.

2.2 Study Design and Treatment Interventions

This is a national, multi-centre, phase III, randomised controlled trial of low or high dose PPI (drug name: Esomeprazole) with or without low dose aspirin for 8 years with expected accrual of 5000 patients. The trial sample size was recalculated to 2500 and some patients re-consented to 10 years follow-up or 28Feb2017 (whichever was the sooner).

The trial is a pragmatic, multi-centre, phase III, randomised, open, 2x2 factorial trial.

ARM A: 20mg PPI Symptomatic treatment only = standard therapy control	ARM B: 80mg PPI Strong acid suppression	No Aspirin (A+B)
ARM C: 20mg PPI Symptomatic treatment and aspirin	ARM D: 80mg PPI Strong acid suppression and aspirin	Aspirin (C+D)
Low dose PPI (A +C)	High dose PPI (B + D)	

AspECT

A phase III randomised study of Aspirin and Esomeprazole chemoprevention in Barrett's metaplasia

Funded by CR-UK, MRC, UHL and NCI

ISRCTN No.85156844

Patients will receive either continuous PPI 20mg/day or continuous PPI 80mg/day with or without aspirin 300mg/day.

If patients are on low dose aspirin for medical reasons (i.e. previous IHD or CVA's rather than self prescribed) they will be randomised to either continuous PPI 20mg/day or continuous PPI 80mg/day arms. They will be allowed to continue to take their aspirin therapy.

Questionnaires dealing with demographics, family history, drug history, smoking, cardiac disease, alcohol, diet and quality of life measures will be completed at baseline. Quality of Life data collection was not possible in all patients and not at all timepoints.

The majority of patients will have an endoscopy at baseline and thereafter at 2 yearly intervals. A number of patients whose baseline endoscopy was more than 12 months before randomisation should have another endoscopy within 6 months of randomisation. A number of patients will have had an endoscopy within the 12 months prior to randomisation. These patients will not have a baseline endoscopy but may have an endoscopy at 2 years from their last endoscopy or 2 years from randomisation at the PI's discretion. These two groups of patients are called retrospective patients.

NOTE on retrospective patients. It is acceptable for primary outcome investigation not to be linked to date of randomisation since we will be using the actual time of an event. Events linked to endoscopy may occur at screenings or during an endoscopy for change of symptoms. Follow-up forms will be completed at yearly intervals from randomisation and QOL forms posted out at 2 yearly intervals from randomisation (for relevant patients).

At each endoscopy any macroscopic abnormality of the Barrett's metaplasia will be biopsied as per local practice and samples taken for formalin fixation and local histological assessment for dysplasia. DNA and RNA will be extracted from the paraffin embedded material for SNP analysis and micro array analysis. In addition an extra biopsy will be taken at each level and snap frozen for genetic studies. In addition to the endoscopy, blood samples will be taken at baseline, between 4 and 6 years, 8 years and at 10 years if the patient consented to extended follow-up, to assess cardiovascular risk factors and the remainder stored for analysis of circulating genetic mutations as and when reliable assays become available.

Patients will come to the hospital pharmacy every 6 months to drop off unused medication and pick up a new 6 month supply.

AspECT

A phase III randomised study of Aspirin and Esomeprazole chemoprevention in Barrett's metaplasia

Funded by CR-UK, MRC, UHL and NCI

ISRCTN No.85156844

The factorial design is efficient due to each patient contributing to the answer to 2 questions. Not only must it be possible for patients to receive both treatments (practically and with consideration of toxicity) but the anticipated treatment effects must be approximately additive. The patients taking part in the PPI only randomisation will be analysed for the PPI primary aim but will not be available for the aspirin primary aim.

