# 7 SAMPLES FOR LABORATORY ANALYSIS

## 7.1 Samples to be analysed in local Trust's laboratories

### ***Pathology***

Biopsy samples are collected from patients participating in the trial. Patients were endoscoped at baseline (the endoscopy prior to randomisation is defined as the baseline visit for patients recruited retrospectively) and thereafter, will be endoscoped at approximately 2 yearly intervals from the date of randomisation (+/- 3 months either side). At each endoscopy any macroscopic abnormality of the Barrett's metaplasia will be biopsied for formalin fixation and histological assessment for dysplasia.

The routine diagnostic pathology samples taken at endoscopy will be labelled, processed and reported according to local hospital protocols.

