6.5 Reliability of data

Survival time will be calculated from date of randomisation to the first of

- date of Barrett's adenocarcinoma
- date of high grade dysplasia
- date of death from any cause

with a censor variable created coded 1 for an event. If none of the above exist for a patient the survival time will be calculated from date of randomisation to

- date of last follow-up

with the censor variable coded 0 to indicate the time does not relate to an event.

This may be done using difference in defined dates in STATA (or similar function/software available at the time of analysis). A random 20 patient manual check will be done to confirm the programming of the calculation.

Other derived variables will have a 20 patient check.

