8.2 Statistical Methods Used for Analysis of Primary Outcome

In the first instance, the primary outcome will be analysed to achieve the primary objectives assuming there is no interaction between treatments.

Kaplan-Meier curves will be produced and logrank analysis will be used to compare the time to primary outcome between those receiving aspirin and those not and also between those receiving low PPI and high dose PPI. A significance level of $p=0.05$ will be used. An accelerated failure time (AFT)

AspECT

A phase III randomised study of Aspirin and Esomeprazole chemoprevention in Barrett's metaplasia

Funded by CR-UK, MRC, UHL and NCI

ISRCTN No.85156844

model will be constructed for each co-primary to adjust the treatment comparisons for age, length of Barrett's metaplasia and presence of intestinal metaplasia (as used in the minimisation procedure). To increase precision, the alternative co-primary will be added into the model. An AFT model was chosen so that the estimates of the effect are in terms of a time ratio (ratio of expected survival times in the aspirin/no aspirin comparison or low PPI/high PPI comparison).

The logrank results will be presented in a table

	total	Number of events	Logrank and p value
Aspirin Aspirin No aspirin			
PPI Low PPI High PPI			

The time ratios will be presented with 95% confidence intervals and will form the definitive analysis for the primary aim.

If proportional hazards assumptions are valid, a Cox regression model with just aspirin treatment and then another with just PPI treatment will be presented. A Cox model for each coprimary considering the effect of treatment whilst adjusting for age, length of Barrett's Metaplasia and presence of intestinal metaplasia will be also be presented. To increase precision, the alternative co-primary will be added into the model. These models will give hazard ratios with associated 95% confidence intervals. These are provided for comparison with other research.

All centres will be analysed together. It is expected that either STATA, SAS, SPLUS or other similar statistical software will be used for the analysis.

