8.8 Supporting information

The withdrawal rates from aspirin and PPI will be described as well as the dose of drug taken at time points throughout the trial.

9. Analysis to address secondary aims

There are many secondary aims so these will be described under each aim

- To assess whether intervention with aspirin results in decreased high-grade dysplasia, in decreased all cause mortality, in decreased adenocarcinoma oesophageal cancer incidence, and in decreased cause-specific mortality when each is considered separately

ANALYSIS: As for primary using the AFT model. As for primary using COX model for all cause mortality. For the COX model for high grade dysplasia, adenocarcinoma oesophageal cancer incidence and cause-specific mortality a competing risks approach will be used since there are expected to be many competing deaths for these endpoints.

For oesophageal cancer, as a sensitivity, the analysis will be rerun including all oesophageal cancers rather than just adenocarcinomas.

- To assess whether intervention with high dose PPI results in decreased high-grade dysplasia, in decreased all cause mortality, in decreased oesophageal cancer incidence and in decreased cause-specific mortality when each is considered separately

ANALYSIS: As for primary using the AFT model. As for primary using COX model for all cause mortality. For the COX model for high grade dysplasia,

AspECT

A phase III randomised study of Aspirin and Esomeprazole chemoprevention in Barrett's metaplasia

Funded by CR-UK, MRC, UHL and NCI

ISRCTN No.85156844

adenocarcinoma oesophageal cancer incidence and cause-specific mortality a competing risks approach will be used since there are expected to be many competing deaths for these endpoints.

For oesophageal cancer, as a sensitivity, the analysis will be rerun including all oesophageal cancers rather than just adenocarcinomas.

- Are there clinical and molecular risk factors than can be identified in BM for the development of BA?

ANALYSIS: Variables to be specified at the end of the trial. These variables of interest will be added to the accelerated failure time model with the event oesophageal adenocarcinoma and those found to be significant will be reported. The variables will also be considered in the competing risk COX approach.;

- What is the cost effectiveness of aspirin and/or PPI treatment in the prevention of BA?

The analysis will not be undertaken by CSM; to be analysed by [name]. Information from protocol:

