Appendix 2: Variables to be used in analysis (Not exhaustive)

To check rand

VARIABLE	FORM
Length of Barrett's at rand or diagnosis	Randomisation or IR patient history
Age at rand	Randomisation
IM	

To describe sample

VARIABLE	FORM
Alcohol consumption	PR Patient history
Smoking history	PR Patient history
Cardiac history	IR Patient history
Duration of Barrett's pre randomisation	IR Patient history
Length of Barrett's at rand or diagnosis	Randomisation or IR patient history
Age at rand	Randomisation

Primary aim

VARIABLE	FORM
Length of Barrett's at rand or diagnosis	Randomisation or IR patient history
Age at rand	Randomisation
Rand date	Randomisation
Last follow-up date	Follow-up form
Date of death	
Cause of death	
Date high grade dysplasia	Endoscopy form or follow-up form
Date adenocarcinoma	Endoscopy form or follow-up form

Secondary aims

VARIABLE	FORM
Cardiac history	IR Patient history
Stage of cancer	Endoscopy report

Document History

Document history AspECT statistical analysis plan		
Ver	Date	Comments
0.1	16 th March 2006	First draft by [name]
0.2	21 st April 2006	Draft for review by [name]
0.3	12 th July 2006	Draft for review by rest of MSG support and [name]
0.4	18 th August 2006	Updated to Jan 2006 version of the protocol Added Info from 20 th July meeting with [name] Added comments/clarifications from 25 th July meeting with MSG support Passed to [name] and [name] to review and sign.
0.5	29 th Sept 2006	Passed to DSMC Added DMC comments Females randomised separately 100 Previous aspirin users to be entered
0.51	15 th August 2007	Added gender to the tables in section 6.2 Previous aspirin use deleted from tables in 6.2 since not collected since June 2007 on shortened forms Analysis of effect of high PPI by each event separately Analysis of effect of aspirin use by each event separately Randomisation to PPI arms only Clarification that Barretts length is at rand if available, otherwise it is at diagnosis Addition to appendix 2 – specifying data needed
0.52	20 th Nov 2007	Changed event list to clarify what cause-specific death means.
0.53	Jan 2008	Added version 9 important changes to randomisation
0.6	30thJan2008	Updated to version 9 of the protocol To be submitted to DSMC April 2008 Logo added on front page
0.7	May 2008	Name of file changed to CSM policy of statistical analysis plan

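### Dating high grade dysplasia to the endoscopy that finds it, as if exact, shrinks the HGD time ratio in any AFT model with a free shape; the composite moves little and the tests hardly at all

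*SAP*

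**What the plan says.** - **Timing of endoscopy.** SAP 2.2: "The majority of patients will have an endoscopy at baseline and thereafter at 2 yearly intervals". Protocol 7.1 gives "approximately 2 yearly intervals from the date of randomisation (+/- 3 months either side". The SAP note on retrospective patients adds: "Events linked to endoscopy may occur at screenings or during an endoscopy for change of symptoms".
- **Date used.** SAP 6.5 runs the survival time to a single "date of high grade dysplasia". SAP Appendix 2 takes that date from the "Endoscopy form or follow-up form". The note in SAP 2.2 justifies visits not linked to randomisation "since we will be using the actual time of an event".
- **Model.** Under SAP 8.2 the AFT time ratios "will form the definitive analysis for the primary aim", with no distribution named. SAP 9 applies the same model to HGD alone: "ANALYSIS: As for primary using the AFT model".
- **Sensitivity analyses.** SAP 8.6 lists many, but none treats HGD as interval-censored. SAP 6.6 recognises that HGD will be under-represented through loss to follow-up, but does not discuss how it is dated.

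**The concern.** HGD is a histological finding, so its onset is never seen. It falls somewhere between the last endoscopy without HGD and the one that shows it. If the finding date is entered as exact, scheduled endoscopies yield almost no HGD before about 21 months (2 years less the 3-month window), and events then arrive in steps. A model with a free shape reads this as a rising hazard.

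The time ratio depends directly on that shape. The SAP chose the AFT model so that effects could be read as a ratio of survival times, and that is the quantity the dating distorts. For HGD, readers could see a hazard ratio near 0.67 beside a time ratio near 1.3 and look for a biological reason, when the visit schedule produced the gap.

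**Working it through.** **1. The plan's effect size.** SAP 2.5.3 gives a control-to-treatment hazard ratio of 1.5, 80% power, two-sided 5%, 196 events and 2224 patients. By Freedman's formula, (1.960 + 0.842)² × (2.5/0.5)² = 7.849 × 25 = 196.2 events; by Schoenfeld's, 4 × 7.849/(ln 1.5)² = 191. With 1% v 0.667% a year, 3 years' accrual, 10 years' further follow-up and exponential loss, N is 2252 (Freedman, 10% lost over 13 years) or 2222 (Schoenfeld, 10% lost over 10 years). The plan's figures are reproduced. Under the exponential assumption made there, a hazard ratio of 1.5 is also a time ratio of 1.5.

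**2. Mechanism.** For a Weibull model, time ratio = 1.5^(1/shape), so the fraction of the log time ratio lost is 1 − 1/shape.
- Shape 1.00 (true onset times): 1.50, none lost.
- Shape 1.43: 1.5^(1/1.43) = 1.33, 30% lost.
- Shape 1.57: 1.5^(1/1.57) = 1.29, 36% lost.

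**3. Simulation inputs.** From the documents: endoscopy every 2 years ± 3 months, death 1.16% a year, adenocarcinoma 0.85% a year, follow-up of 8 to about 10 years. Assumed: HGD 0.5% a year (range 0.25% to 1%), since SAP 2.5.3 found no good UK estimate; constant onset hazard; the same effect of 1.5 on every component; endoscopy always detects HGD. Large samples (160,000 to 400,000 patients per scenario) were fitted by maximum likelihood. Loss below is 1 − ln(estimate)/ln(true-date estimate).

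**4. HGD alone**

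| Scenario | True onset dates | Finding dates | Log ratio lost |
|---|---|---|---|
| Weibull, 0.5% a year | 1.50 | 1.33 (shape 1.43) | about 30% |
| Weibull, other follow-up assumptions | 1.50 | 1.29 to 1.32 | 37% to 32% |
| Log-logistic | 1.50 | 1.34 | 28% |
| Log-normal | 1.58 | 1.36 | 33% |
| Half of patients' visits up to 1 year early | 1.52 | 1.35 | 28% |
| 30% of HGD dated exactly | 1.49 | 1.38 | 20% |
| Exponential | 1.50 | 1.50 | none |

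The HGD rate hardly matters: 0.25% to 1% a year gives 1.33 to 1.34. If the onset hazard is not constant, a true shape of 1.5 moves the ratio from 1.32 to 1.24 (23% lost) and a true shape of 0.7 from 1.71 to 1.37 (41% lost). An interval-censored Weibull fit to the base case returns 1.50 with shape 1.00.

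**5. Composite (Weibull)**

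| Scenario | True onset dates | Finding dates | Log ratio lost |
|---|---|---|---|
| Base case | 1.49 | 1.46 | 5% |
| Smallest shift (true HGD shape 1.5) | 1.462 | 1.452 | 2% |
| True HGD shape 0.7 | 1.549 | 1.479 | 11% |
| HGD 1% a year | 1.50 | 1.43 | 12% |
| No effect on death | 1.221 | 1.204 | 7% |
| Adenocarcinoma also found only at endoscopy | 1.515 | 1.428 | 14% |

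A separate run of the last scenario gave 1.37 to 1.39 against 1.49 to 1.50, about 20%. Both are upper bounds, since SAP 6.6 says registry flagging also captures cancers.

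**6. Trial-size check.** Over 150 trials of 2500 patients (mean 80 HGD and 425 composite events), HGD averaged 1.33 by finding date and 1.50 interval-censored. Mean log ratio over its standard deviation was 1.44 v 1.40. For the composite, finding dates gave 1.47 and true onset dates 1.51, with 3.65 v 3.62. The composite shift is ln 1.506 − ln 1.470 = 0.024, against a standard deviation of 0.106. The size of the estimate moves; the strength of evidence does not.

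**The case against.** The other side has substance.

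- **The sentence in SAP 2.2.** A reader might infer that the SAP claims to observe onset. In context it is a note on retrospective patients, saying that recorded dates are used rather than visits tied to randomisation. Time to diagnosed HGD is a legitimate endpoint, and nowhere does the SAP target latent onset. This stands; only the wording misleads.
- **The primary result.** A reader might infer that the trial's main conclusion is at risk. It is not: the composite moves by about a quarter of one standard deviation, and the logrank test, Cox models and competing-risks analysis of HGD are planned as well.
- **The distribution.** The bias needs a free shape or scale, and SAP 8.2 commits to neither that nor an exponential. This stands as a condition. It is no defence, because detection-dated HGD would itself give a Weibull shape near 1.4 to 1.5 and so speak against an exponential.
- **Shorter intervals.** Symptom-driven endoscopies, repeat endoscopy within 6 months of randomisation for some retrospective patients, and closer surveillance after low grade dysplasia (Protocol 6.4) all narrow the gap. Dating 30% of HGD exactly still leaves a 20% loss.
- **Interval censoring is not always better.** It assumes that a negative endoscopy excludes HGD. With 70% or 50% biopsy sensitivity it gave 1.42 or about 1.35, still closer to 1.50 than finding dates (1.27 or 1.23). But with half the patients retrospective and HGD able to arise before randomisation, it gave 1.59 against 1.38. With a mixed irregular schedule it gave 1.66 against 1.46 (simulation error about 0.03). A reader might infer that it should replace the definitive analysis; these runs do not support that.
- **Data.** Last-negative dates may be missing. The HGD date may come from a follow-up form, patients may withdraw from endoscopy (Protocol 6.2), and the unscheduled forms in the Protocol's schedule of events do not include an endoscopy form.

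**Conclusion.** The point holds for the size of the HGD time ratio. With a true ratio of 1.50, constant onset hazard and an assumed HGD rate of 0.25% to 1% a year, the planned AFT analysis of HGD alone would give about 1.29 to 1.38 if the chosen distribution has a free shape or scale. The composite loses about 2% to 12% of its log time ratio, with 14% to 20% as an upper bound. An exponential AFT would show nothing, and there is no bias if the true effect is nil. The reading that HGD is dated to the finding endoscopy rests on the single-date definition in SAP 6.5 and the form source in Appendix 2; the SAP does not say so outright. The documents give neither the HGD rate nor the share of symptom-driven endoscopies. This calls for an added analysis and clearer wording, not a new primary analysis.

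**What to change.** 1. **SAP 8.2:** name the AFT distribution, or the rule for choosing it.
2. **SAP 9:** report the HGD time ratio from an interval-censored AFT (last negative to first positive endoscopy) beside the detection-date fit, for both the aspirin and the PPI comparisons.
3. **SAP 8.6:** add an interval-censored AFT for the composite as a sensitivity analysis, with HGD and surveillance-detected cancers as intervals and deaths exact. Keep the detection-date analysis as primary.
4. **Rules to state:** how missing last-negative dates are handled, and how patients not endoscoped at randomisation enter the interval-censored fit.
5. **SAP 2.2:** reword the note to say that the date of diagnosis is used.

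The cost is one derived variable (date of last negative endoscopy) and some programming; standard software such as STATA stintreg or SAS LIFEREG fits these models. Endoscopy forms are scheduled at baseline and every 2 years (SAP 2.8), so many interval limits should already be held. The price is reliance on a negative endoscopy excluding HGD, which should be stated with the result.
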